#### **4.4 Exploratory Endpoints**

The exploratory endpoints include the following:

*During the 12-month double-blind ALN-controlled study period:*

- Subject incidence of new or worsening vertebral fracture through Month 12
- Subject incidence of major nonvertebral fracture (pelvis, distal femur, proximal tibia, ribs, proximal humerus, forearm, and hip) through Month 12
- Subject incidence of multiple new or worsening vertebral fractures through Month 12
- Actual value in PRO and ClinRO measures (OPAQ SV, EQ-5D-5L, LAD, and BPI worst pain) at Months 6 and 12
- Change from baseline in PRO and ClinRO measures (OPAQ SV, EQ-5D-5L, LAD, and BPI worst pain) at Months 6 and 12
- Actual value in PRO and ClinRO measures after experiencing a nonvertebral or clinical vertebral fracture (OPAQ SV, EQ-5D-5L, LAD, and BPI worst pain) at reporting of the nonvertebral or clinical vertebral fracture and at 1, 2 and 3 months afterwards
- Change from pre-fracture baseline in PRO and ClinRO measures after experiencing a nonvertebral or clinical vertebral fracture (OPAQ SV, EQ-5D-5L, LAD, and BPI worst pain) at reporting of the nonvertebral or clinical vertebral fracture and at 1, 2 and 3 months afterwards
- Proportion of subjects with a clinically meaningful improvement in worst pain (defined as a 2-point improvement in the BPI worst pain scale compared with the fracture reporting visit) at 1, 2, and 3 months after reporting of a nonvertebral or clinical vertebral fracture
- Change from baseline in height at Month 12

*During the primary analysis period:*

- Subject incidence of major osteoporotic fracture (hip, forearm, humerus, and clinical vertebral) at primary analysis
- Actual value in PRO and ClinRO measures (OPAQ SV, EQ-5D-5L, LAD, and BPI worst pain) at Months 18, 24, 30, and 36
- Change from baseline in PRO and ClinRO measures (OPAQ SV, EQ-5D-5L, LAD, and BPI worst pain) at Months 18, 24, 30, and 36
- Change from baseline in height at Month 24

*During the month 12 to 24 ALN study period*

- Subject incidence of new vertebral fractures between Month 12 and Month 24
- Subject incidence of clinical fracture (nonvertebral fracture and clinical vertebral fracture) between Month 12 and Month 24
- Subject incidence of nonvertebral fracture between Month 12 and Month 24
- Subject incidence of hip fracture between Month 12 and Month 24
- Subject incidence of clinical vertebral fracture between Month 12 and Month 24

#### **4.5 Imaging and PK/BTM/Biomarker Sub-study Endpoints**

*During the 12-month double-blind ALN-controlled study period:*

- Romosozumab serum concentrations at Day 1, Months 1, 3, 6, 9, and 12
- Percent change from baseline in P1NP, BSAP, OC, and sCTX at Months 1, 3, 6, 9, and 12
- Percent change from baseline in iPTH and sclerostin at Months 1, 3, 6, 9, and 12
- For subjects participating in the imaging components:
  - Percent change from baseline in integral (total) and trabecular vBMD at the lumbar spine by QCT at Months 6, and 12
  - Percent change from baseline in lumbar spine strength as assessed by FEA at Months 6, and 12
  - Percent change from baseline in DXA BMD at the lumbar spine, total hip, and femoral neck at Month 6

*During the primary analysis period:*

- Percent change from baseline in P1NP and sCTX at Months 15, 18, 24, and 36
- Percent change from baseline in iPTH and sclerostin at Months 15, 18, 24, and 36
- For subjects participating in the imaging components:
  - Percent change from baseline in integral (total) and trabecular vBMD at the lumbar spine by QCT at Months 24

- Percent change from baseline in lumbar spine strength as assessed by FEA at Months 24
- Percent change from baseline in DXA BMD at the lumbar spine, total hip, and femoral neck at Month 18

#### 4.6 Planned Covariates

All analyses assessing treatment effect of new vertebral fracture, clinical fracture or nonvertebral fracture will include the stratification factor (age < 75 or ≥ 75 years), presence or absence of severe vertebral fracture at baseline, and baseline total hip BMD T-score as main covariates in the model. Additional covariates will be analyzed separately and simultaneously, if appropriate, as exploratory analyses. The additional covariates of interest include the following:

- baseline body mass index (BMI)
- years since menopause at baseline
- prior (history) nonvertebral osteoporotic fracture (yes, no)
- geographic region:
  - Western Europe and New Zealand/Australia
  - Central and Eastern Europe and Middle East
  - Asia Pacific and South Africa
  - North America (including Canada, and United States)
  - Central/Latin America
- race/ethnicity (white and non-white)
- prior use of bone-specific therapeutic agents (yes, no)
- 10-year probability of major osteoporotic fracture with BMD (FRAX, as calculated by third-party vendor)
- baseline lumbar spine BMD T-score

#### 5. Hypotheses and/or Estimation

The primary clinical hypotheses are that romosozumab treatment for 12 months followed by ALN treatment compared with ALN treatment alone is effective in reducing the incidence of clinical fracture (nonvertebral fracture and clinical vertebral fracture) and new vertebral fracture in postmenopausal women with osteoporosis. It is expected that romosozumab treatment for 12 months followed by ALN treatment will reduce the incidence of clinical fractures by 30% and the incidence of new vertebral fractures by 50% compared with the control group (ALN alone).

The primary safety hypothesis is that romosozumab treatment for 12 months is well tolerated in postmenopausal women with osteoporosis.

## **6. Definitions**

### **6.1 Basic Definitions**

#### **Investigational Product (IP)**

Romosozumab, ALN and the respective matched placebo

#### **Interactive Voice Response System (IVRS)**

The system used to assign screened subjects to randomized treatment as well as to manage the supply of double-blind romosozumab and ALN, as well as the open-label ALN to the site and track subject study termination data

#### **6.1.1 Study Points of Reference**

##### **Baseline**

Baseline is the closest recorded measurement before the administration of the first dose of investigational product. If the measurement is done on the same day as the first dose and the exact measurement time relative to the first dose is unknown, it will be assumed the measurement is done before the administration of the first dose of investigational product. If a subject does not receive investigational product, baseline is the closest recorded measurement on or before the enrollment (randomization) date.

Note: If baseline result from lateral spine x-ray, DXA, or QCT assessment is not available, the result assessed on or before Study Day 14 will be considered baseline.

##### **Pre-fracture Baseline for PRO/ClinRO Endpoints**

Pre-fracture baseline for PRO/ClinRO endpoints is the closest recorded PRO/ClinRO measurements before the visit of reporting a nonvertebral fracture or clinical vertebral fracture.

##### **PRO/ClinRO Endpoints at Report of Fracture**

PRO/ClinRO Endpoints at Report of Fracture is the first recorded PRO/ClinRO measurements within 45 days after the date of the reported non-vertebral fracture or clinical vertebral fracture.

##### **Study Day 1**

The first day of investigational product administration or the day of randomization for subjects who were not administered any dose of investigational product

## Study Day

The number of days from Study Day 1, inclusive:

$$\text{Study Day} = (\text{Date of Interest} - \text{Date of Study Day 1}) + 1$$

## Visit Windows

Based on protocol, all monthly study visits through Month 12, during the 12-month double-blind ALN-controlled study period, have a  $\pm 7$ -day window. The study visits during the open-label ALN study period, have a  $\pm 14$ -day window. Study procedures for a specific visit may be completed on multiple days as long as all the procedures are completed within the visit window. To allow for variations in scheduling, the analysis visit windows defined in [section 13.1.1](#) will be used to assign evaluations to a most appropriate nominal visit for analysis and summarization.

### 6.1.2 Study Dates

#### Informed Consent Date

The date on which a subject signed the informed consent

#### Enrollment (Randomization) Date

The date on which a subject is assigned to **one** of the treatments through the IVRS

#### End of Primary Analysis Period Date

The date on which clinical fracture events have been confirmed for at least 330 subjects and after all randomized subjects have had the opportunity to complete the Month 24 visit. For subjects who withdraw before this date, then their End of Study Date is used.

#### End of Final Analysis Period Date

If the study will continue to the final analysis, the date on which nonvertebral fracture events have been confirmed for at least 440 subjects if statistical significance of non-vertebral fractures is not demonstrated at primary analysis. For subjects who withdraw before this date, then their End of Study Date is used.

#### End of Study Date

The date recorded on the End of Study eCRF

#### First Dose Date

The date of administration of first dose of investigational product (ie, the first date recorded on the Investigational Product Administration eCRF for romosozumab or placebo with volume > 0 or the first dose date of ALN or placebo in

Alendronate/Placebo Dispensation eCRF with the number of tablets taken > 0, whichever is earlier), which may or may not be the same as the randomization date

#### **Last Double-blind SC Dose Date**

The date of administration of the last SC investigational product (ie, the last date recorded on the Investigational Product Administration eCRF for romosozumab or placebo with volume > 0)

#### **Last Double-blind Oral Dose Date**

The date collected on the End of Blinded Alendronate Administration eCRF

#### **Last Dose Date in Double-blind Period**

The date of last double-blind SC dose date or the last double-blind oral dose date, whichever is later

#### **First Open-label ALN Dose Date**

The date collected on the First Dose of open-label Alendronate Dispensation eCRF

#### **First Open-label ALN Dispensation Date**

The date of dispensation of ALN collected on the Month 12 Alendronate Dispensation eCRF

#### **Last Open-label ALN Dose Date**

The date of last alendronate administration recorded in End of Alendronate Administration eCRF

#### **End of Double-blind Period Date**

End of the double-blind period date is defined as the following:

1. First open-label ALN dose date if this date is prior to or on Study Day 366 + 30 days
  2. Month 12 visit date if subject did not receive the open-label ALN prior to or on Study Day 396 and this date is prior to or on Study Day 396 days
  3. End of study day or Study Day 396, whichever occurs first, for subjects who did not complete the Month 12 visit prior to study day 396 days
- The Month 12 visit date is defined as the latest assessment collected at Month 12.

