## Study Glossary

Abbreviation or Term	Definition/Explanation
ALN	Alendronate
ALP	Alkaline Phosphatase
ALT (SGPT)	Alanine Aminotransferase (Serum Glutamic Pyruvic Transaminase)
AMG 785 (romosozumab)	Anti-human sclerostin antibody, also referred to as hu13C7, h13C7, or Mab-B
ARCH	Active-controlled Fracture Study in Postmenopausal Women with Osteoporosis at High Risk of Fracture
AST (SGOT)	Aspartate Aminotransferase (Serum Glutamic Oxaloacetic Transaminase)
BMD	Bone Mineral Density
BMI	Body Mass Index
BPI	Brief Pain Inventory
BSAP	Bone Specific Alkaline Phosphatase
BTM	Bone Turnover Marker
BUN	Blood Urea Nitrogen
ClinRO	Clinician Reported Outcome; questionnaires completed by physician or site staff using information provided by the subject
CTCAE	Common Terminology Criteria for Adverse Events
Date of Randomization	Date on which the randomization number is assigned; synonymous with enrollment date
DILI	Drug-Induced Liver Injury
DMC	Data Monitoring Committee; term synonymous with Data Safety Monitoring Board
DXA	Dual energy X-ray Absorptiometry
eCRF	Electronic Case Report Form
EDC	Electronic Data Capture
Electronic Trial Operations System	An electronic system that is used to facilitate the operations of a clinical trial through the collection of study related data. Most common applications of an Electronic Trial Operations system within a clinical trial are: subject randomization and investigational product management. Term synonymous with the industry term IVRS.
End of study for individual subject	Defined as the last day that protocol-specified procedures are conducted for an individual subject
End of study (primary completion)	Defined as the time when the last subject is assessed or receives an intervention for the purposes of final collection of data for the primary outcomes
End of study (end of trial)	Defined as when the last subject is assessed or receives an intervention for evaluation in the study
EQ-5D-5L	EuroQoL-5 Dimensions-5 Levels Health Survey

Abbreviation or Term	Definition/Explanation
eSAE	Electronic Serious Adverse Event
ET	Early Termination
FDA	Food and Drug Administration
FEA	Finite Element Analysis
GCP	Good Clinical Practice
ICF	Informed Consent Form
ICH	International Conference on Harmonisation
IEC	Independent Ethics Committee
IRB	Institutional Review Board
IP	Investigational Product
IPIM	Investigational Product Instruction Manual
iPTH	intact Parathyroid Hormone
IV	Intravenous

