#### **9.1.2 Reporting Procedures for Adverse Events**

The investigator is responsible for ensuring that all adverse events observed by the investigator or reported by the subject that occur after the first dose of IP through the end of study are reported using the applicable eCRF (eg, Adverse Event Summary eCRF). For subjects who discontinue the study early, adverse events will be reported through 30 days after the last dose of IP.

The investigator must assign the following adverse event attributes:

- Adverse event diagnosis or syndrome(s), if known (if not known, signs or symptoms),
- Dates of onset and resolution,
- Severity (and/or toxicity per protocol),
- Assessment of relatedness to IP, and
- Action taken.

The adverse event toxicity grading scale used will be the Common Terminology Criteria for Adverse Events (CTCAE) version 3.0. The toxicity grading scale used in this study is described in [Appendix B](#).

The investigator must assess whether the adverse event is possibly related to the IP and/or other study drugs. This relationship is indicated by a "yes" or "no" response to the question: Is there a reasonable possibility that the event may have been caused by the IP and/or other study drugs?

The investigator must assess whether the serious adverse event is possibly related to any study-mandated screening procedure. This relationship is indicated by a “yes” or “no” response to the question: “Is there a reasonable possibility that the event may be related to screening procedures?”

The investigator must assess whether the adverse event is possibly related to any study-mandated activity or procedure. This relationship is indicated by a “yes” or “no” response to the question: “Is there a reasonable possibility that the event may have been caused by a study activity/procedure”?

The investigator is responsible for reviewing laboratory test results and determining whether an abnormal value in an individual study subject represents a clinically significant change from the subject’s baseline values. In general, abnormal laboratory findings without clinical significance (based on the investigator’s judgment) should not be recorded as adverse events. However, laboratory value changes that require treatment or adjustment in current therapy are considered adverse events. Where applicable, clinical sequelae (not the laboratory abnormality) should be recorded as the adverse event.

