### **9.2.2 Reporting Procedures for Serious Adverse Events**

The investigator is responsible for ensuring that all serious adverse events observed by the investigator or reported by the subject that occur after signing of the informed consent through 30 days after the last dose of IP are recorded in the subject’s medical record and are submitted to Amgen. For subjects who discontinue the study early, serious adverse events will be reported through 30 days after the last dose of IP. The serious adverse event must be submitted to Amgen within 24 hours following the investigator’s knowledge of the event. If the electronic data capture (EDC) system is unavailable to the site staff to report the Serious Adverse Event, the information is to be reported to Amgen via an electronic Serious Adverse Event (eSAE) Contingency Report Form within 24 hours of the investigator’s knowledge of the event. See [Appendix D](#) for a sample of the Serious Adverse Event Worksheet/eSAE Contingency Report Form. Where the first notification of a Serious Adverse Event is reported to Amgen via the eSAE Contingency Report Form, the data must be entered into the EDC system when the system is again available.

The investigator is expected to follow reported serious adverse events until stabilization or reversibility.

In addition to the attributes listed in [Section 9.1.2](#), the investigator must also complete the SAE section of the Adverse Event Summary CRF.

After the protocol-required reporting period defined above, the investigator does not need to actively monitor subjects for serious adverse events. However, if the investigator becomes aware of a serious adverse event after this protocol-required reporting period, the investigator will report the event to Amgen within 24 hours following the investigator’s knowledge of the event. SAEs reported outside of the

protocol-required reporting period will be captured within the safety database as clinical trial cases for the purposes of expedited reporting.

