 11. Blood draws for BTMs must be obtained from subjects in fasting stage and before noon. Fasting stage is defined as overnight fasting. If overnight fasting is not feasible, at a minimum 8 hours is required.

12. SAE reporting to continue through 30 days after the last dose of IP.
13. Monthly contacts begin at M13. Contact will be initiated by a phone call. During the primary analysis period, if back pain is reported during the phone call, it will be recorded as an adverse event and the subject will be asked to complete an unscheduled follow-up clinic visit as soon as possible but no later than 21 days after reporting of the back pain for evaluation of a suspected clinical vertebral fracture.
14. Lateral spine x-ray will only be taken at the unscheduled follow-up clinic visit if the investigator considers the back pain previously reported during the monthly phone contact to be possibly due to a new or worsening vertebral fracture.
15. To facilitate subject scheduling, the Day 1/baseline lumbar spine DXA scan may be taken with the proximal femur DXA scan performed during screening. For Screening and Day 1 purposes, lateral spine x-rays and DXA scans of the lumbar spine and proximal femur taken up to 35 days prior to the beginning of the screening period may be used if all of the criteria outlined in [Section 7.2.1](#) are met.
16. In a subset of subjects.
17. To be processed and sent to the central laboratory during the primary analysis period; to be analyzed at local laboratories following the primary analysis period.
18. To be performed in the primary analysis period only.
19. To be performed at month 36 and then every 12 months thereafter during the primary analysis period only.
20. For subjects in the sub-study only.

Notes:

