### **Open-label ALN Period**

The time period from the end of double-blind period date to the end of study date, inclusive

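### Adverse events collected up to 30 days after the last dose in women who leave the study early have no assigned place in the SAP's safety periods, tables or listings if the End of Study Date is the day of exit

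*SAP*

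**What the plan says.** **What is collected.** Protocol 9.1.2: "For subjects who discontinue the study early, adverse events will be reported through 30 days after the last dose of IP". Protocol 9.2.2 repeats this for serious events: "For subjects who discontinue the study early, serious adverse events will be reported through 30 days after the last dose of IP". A footnote to the Schedule of Assessments (Protocol Appendix A) gives the same SAE window without limiting it to early leavers: "SAE reporting to continue through 30 days after the last dose of IP". Protocol 7.9 sends all deaths, and serious events of possible cardiovascular origin, to independent adjudication.

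**Where the SAP periods end for a woman who leaves early.**
- Double-blind period (SAP 6.1.2, item 3): "End of study day or Study Day 396, whichever occurs first, for subjects who did not complete the Month 12 visit". Items 1 and 2 can close it at the first open-label ALN dose or the Month 12 visit.
- Primary analysis period (SAP 6.1.2): "For subjects who withdraw before this date, then their End of Study Date is used". The final analysis period has the same rule.
- Open-label ALN period (SAP 6.1.3): "The time period from the end of double-blind period date to the end of study date, inclusive". The on-study period also stops at the End of Study Date.

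**What the tables count.** SAP 7.5 and 10.6.1 count double-blind events. They add later events, within the period, only for women who took at least one open-label ALN dose. SAP 10.6 plans two AE listings: one for women with no active dose, and one for treated women who stayed on study without open-label ALN.

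**What the End of Study Date is.** SAP 6.1.2 says only "The date recorded on the End of Study eCRF". The protocol's Study Glossary describes an individual subject's end of study as "Defined as the last day that protocol-specified procedures are conducted for an individual subject".

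**The concern.** The protocol ties collection to the last dose, and the SAP ties its safety periods to the End of Study Date. Where the first date falls later, the protocol gathers events that the SAP does not assign to any table or listing.

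Take a woman injected at Month 5 (about Day 151) who leaves a week later, for a reason other than full withdrawal of consent, and has a myocardial infarction 15 days after exit. The event is reportable and goes for adjudication. If her End of Study Date is the day she left, her double-blind, primary analysis and on-study periods have all closed. She took no open-label ALN, so nothing later is counted for her. Neither listing covers a treated woman who has left.

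The time just after an exit that may be related to illness, with recent exposure to study drug, matters for safety. The adjudicated cardiovascular events in SAP 10.6.3 are summarised as incidence and odds ratios, so a few omitted events could be visible. SAP section 11 records no departure from the protocol here, and SAP 10.6.1 uses the term treatment-emergent without a definition that would bring these events in.

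**Working it through.** The plan states no figure on this point, so there is nothing to reproduce. The check compares dates and then bounds the gap.

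**Step 1: the gap for one woman.** Uncovered days = max(0, last IP dose date + 30 − End of Study Date). With the last dose on Day 151, collection runs to Day 181:

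| End of Study Date | Uncovered days |
|---|---|
| Day 152 | 29 |
| Day 158 | 23 |
| Day 165 | 16 |
| Day 181 or later | 0 |

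In the example she exits on Day 158 and the event falls on Day 173. That is after every SAP period has closed and before collection ends. A weekly tablet taken after the injection would only move the end of collection later.

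**Step 2: which date is on the eCRF.** SAP 6.1.2 leaves it open. Four places favour the exit date:
- the glossary's link to the last protocol-specified procedures;
- Protocol Appendix A note d, which has early-termination procedures done when the woman leaves, with no contact scheduled at last dose + 30 days;
- the use of this date in SAP 6.1.2 as the stop date for women who withdraw;
- SAP 9.2.6, which treats a death date as the End of Study date.

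**Step 3: ceiling for year 1.** Inputs are about 4,000 women (Protocol 3.3) and 10% first-year dropout (Protocol 10.2). Assume that the eCRF date is the exit date and that every leaver was dosed on the day she left.
- 10% as a proportion: 400 leavers × 30/365.25 = 32.9 woman-years.
- 10% as a hazard: 4,000 × (1 − e^−0.10) = 381 leavers, giving 31.3 woman-years.
- Last tablet 7 days before exit (23 days left): 25.2 and 24.0 woman-years.
- Year-1 exposure: 4,000 × 0.10/(−ln 0.9) = 3,796 woman-years. Share: 32.9/3,796 = 0.87%.

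**Step 4: ceiling by the primary analysis.** Further inputs are 34 months' enrollment (assumed uniform), a primary analysis when the last woman reaches Month 24, and 8% yearly dropout after year 1. Follow-up is then 24 to 58 months.
- Still on study at t years (t > 1): 0.9 × 0.92^(t−1).
- Average over t = 2 to 4.833: 0.9/(−ln 0.92) × (0.9200 − 0.7264)/2.833 = 0.7375. So 26.3%, about 1,050 women, have left.
- 1,050 × 30/365.25 = 86 woman-years.
- Mean exposure per woman: 0.949 + 10.794 × (1 − 0.7375/0.9) = 2.90 years, or about 11,600 woman-years in all. Share: 86/11,600 = 0.7%.

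**Step 5: floor.** If the End of Study eCRF is dated when the 30-day reporting ends, the gap is zero.

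**The case against.** The strongest reply is that the loss rests on an unstated premise. A reader might infer that post-exit events certainly enter no table. The documents do not support that: if sites date the End of Study form at the end of the 30-day reporting, every such event falls inside the periods. This stands as a condition. It does not remove the point, because the SAP would still need to say so, and the text leans towards the exit date.

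Other objections also stand in part.
- **Consent.** After full withdrawal of consent, Protocol 8.1 includes data only up to withdrawal, so exclusion agrees with the protocol. Other reasons for removal in the same section, such as an adverse event, noncompliance or an administrative decision, are not of this kind.
- **Stopping drug is not leaving.** Protocol 6.5 and 8.1 keep women who stop IP on the visit schedule, and their events continue to count. A woman whose last dose was more than 30 days before exit loses nothing.
- **Deaths.** It is tempting to say that deaths are understated. SAP 9.2.6 equates the death date with the End of Study date, so a death that is itself the exit does not fall after the period. Events on the closing day are a separate matter.
- **Unequal bias.** A reader might infer bias between arms. No figure in the documents shows that exits differ by arm. After Month 12 both arms are on open-label ALN, which covers about 650 of the 1,050 leavers (1,050 − 400).
- **Size.** The totals credit every leaver with a full 30 days, although some die, are lost to follow-up or withdraw consent.

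**Conclusion.** The mismatch is real and unreconciled. The protocol collects to last dose + 30 days, and no SAP safety period for an early leaver runs past her End of Study Date. It would be too strong to say that every period closes on that date, since the double-blind period can close earlier.

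Whether events are lost depends on the eCRF date being the exit date, which is the more natural reading but is not stated. On that reading, events with onset after exit and within 30 days of the last dose are collected, and adjudicated where they qualify, but reach no AE or cardiovascular table and no listing. This affects only women who leave within 30 days of a dose and have not fully withdrawn consent.

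The uncovered time is between zero and about 33 woman-years in year 1, and between zero and about 86 by the primary analysis. The upper figures are ceilings that rest on the planning dropout rates, not estimates of lost follow-up. Both are under 1% of exposure. The point merits correction because the data are already collected and the time follows recent exposure, not because a material bias has been shown.

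**What to change.** For safety analyses only, amend SAP 6.1.2, 7.5 and 10.6:

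1. For women who discontinue the study early, count events with onset through the later of the End of Study Date and the last IP dose date + 30 days. Attribute them to the period of the last dose (double-blind if no open-label ALN was taken).
2. Cap this at death, last contact or full withdrawal of consent. Without the cap, the rule would add unobserved time, or time that Protocol 8.1 does not include.
3. Extend subject-years (SAP 6.3) only over that observed, includable time.
4. State how the End of Study eCRF date is set for early leavers, and define treatment-emergent to match.

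Leave the efficacy periods and censoring dates unchanged. The cost is a few sentences and some programming of the period ends; no new data are needed. The small downside is that safety and efficacy periods will end on different dates for these women.
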